## **7. SAFETY ANALYSIS**

### **7.1. Part A**

#### **7.1.1. General**

The safety population will be used for all safety summaries. Summaries will be presented by parent study treatment group and overall. Summaries will be presented for Parts A and B combined unless otherwise noted.

#### **7.1.2. Study Drug Administration**

Duration of treatment (days treated) is the number of days on treatment based on the first and last day of treatment with the study drug (last day of study drug – first day of study drug + 1). Weeks on treatment using the categories  $\geq 2$  weeks,  $\geq 4$  weeks,  $\geq 6$  weeks,  $\geq 15$  weeks,  $\geq 28$  weeks,  $\geq 41$  weeks,  $\geq 54$  weeks,  $\geq 67$  weeks,  $\geq 80$  weeks,  $\geq 93$  weeks,  $\geq 106$  weeks,  $\geq 119$  weeks,  $\geq 132$  weeks,  $\geq 145$  weeks,  $\geq 158$  weeks and  $\geq 171$  weeks will be summarized using descriptive statistics. Duration of treatment (days) will also be summarized as continuous data using descriptive statistics.

Total daily dose (mg) will be summarized as continuous data at each Part A visit using descriptive statistics. In addition, total daily dose (mg) will be summarized by individual dose and dose categories ( $< 24$  mg,  $\geq 24$  to  $\leq 36$  mg,  $> 36$  to  $\leq 48$  mg, and  $> 48$  mg) as categorical data at each Part A visit using descriptive statistics.

Percent treatment compliance is calculated as  $100 \times (\text{number of tablets used} / \text{number of tablets expected to be used})$ . The number of tablets used is the number of tablets dispensed minus the number of tablets returned. If a patient does not return the pill bottle, it will be assumed that the patient took no study medication from that bottle for the purposes of calculating compliance. The number of tablets expected to be used is based on the number of morning and evening dosing times during the treatment period (1 tablet is used for each dosing time point). A patient will be deemed compliant over the treatment period if the patient has taken 80% to 105% of the expected tablets of study drug.

Percent treatment compliance will be summarized as continuous data using descriptive statistics. In addition, percent treatment compliance will be summarized as categorical data using descriptive statistics for the following categories:  $< 80\%$ , 80% to 105%,  $> 105\%$ .

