### 5.1. Study Drug

#### 5.1.1. SD-809

The study drug is a matrix formulation in the form of a tablet to be administered with food. Study drug is coated with a polymer coating to aid in swallowing. SD-809 tablets have been manufactured according to current Good Manufacturing Practices regulations.

During titration/dose adjustment in Part A, SD-809 tablets will be labeled according to applicable regulatory guidelines and supplied in weekly blister packs as 6, 9, 12, 15, and/or 18 mg tablets. Each blister pack will contain a sufficient supply of study drug until the next specified visit, plus overage to account for potential delays in study visits or evaluations or receipt of their supplies. **During long-term treatment, SD-809 will be supplied in 30-count bottles and labeled according to applicable regulatory guidelines.** During the 1-week double-blinded Randomized Withdrawal Period, SD-809 will be supplied in 20-count bottles and labeled according to the applicable regulatory guidelines.

During Part C, SD-809 will be supplied in 30-count bottles.

Complete details regarding SD-809 supply, dispensing, and ordering will be provided in the study Operations Manual.

SD-809 tablets must be stored in a secure area with access limited to authorized staff, protected from light at controlled room temperature, 15°C to 25°C (59°F to 77°F).

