**5.5. Study Drug Compliance**

The Investigator or designated study staff is responsible for monitoring the subject's compliance with study drug during the trial. Compliance will be assessed by tablet count, i.e., evaluation of returned study drug blister cards/bottles (e.g., amount used/amount expected to be used in interval between visits) and must be reviewed at every visit while the subject is still in clinic to determine if the subject is taking study drug as directed.

Compliance will be evaluated by calculating the number of tablets used (tablets dispensed minus tablets returned) divided by the expected number of tablets to be used. A subject will be deemed compliant over the overall treatment period if the subject has taken 80% to 105% of the expected tablets of study drug.

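### SAP 7.1.2 scores an unreturned bottle as no drug taken but keeps its dosing days in the denominator, so some adherent patients can be tabulated below 80% compliance

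*SAP*

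**What the plan says.** Protocol 5.5 defines compliance as the "number of tablets used (tablets dispensed minus tablets returned) divided by the expected number of tablets to be used". It relies on inspection of returned blister cards and bottles at each visit and gives no rule for a container that does not come back.

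SAP 7.1.2 uses the same numerator: "The number of tablets used is the number of tablets dispensed minus the number of tablets returned". It then adds the exception: "If a patient does not return the pill bottle, it will be assumed that the patient took no study medication from that bottle". The denominator is every morning and evening dosing time in the treatment period, on the basis that "1 tablet is used for each dosing time point". Nothing is deducted for dosing times covered by an unreturned bottle. The threshold is the protocol's: "A patient will be deemed compliant over the treatment period if the patient has taken 80% to 105% of the expected tablets". The result is summarised as a continuous variable and in three categories: below 80%, 80% to 105%, above 105%.

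Drug comes in two kinds of container. In titration it is "supplied in weekly blister packs as 6, 9, 12, 15, and/or 18 mg tablets" (Protocol 5.1.1). Later, "During long-term treatment, SD-809 will be supplied in 30-count bottles". The SAP exception names only the bottle.

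SAP Section 9 lists one departure from the protocol, about ECG variables. The SAP Introduction says that the SAP prevails where the two documents differ and that differences will be explained in the study report.

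**The concern.** Take a 30-count bottle that never comes back. Dispensed minus returned counts 30 tablets used; the exception counts none. Because the denominator is untouched, the error has one direction.

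The rule is also uneven. An unreturned titration blister pack is outside the exception, so it still counts as fully used, while an unreturned bottle counts as fully unused. One percentage can contain both. It also sits awkwardly with the SAP's exposure accounting: duration of treatment runs from first to last dosing day, so days that count as treated in patient-years can count as no tablets taken in compliance.

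At stake is the meaning of the below-80% row. A reader of a long-term safety report uses it to judge how many patients took the drug as directed. Under this rule it merges non-adherence with missing containers.

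**Working it through.** The plan states no figure on this point to reproduce, so the rule is applied directly.

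**Inputs from the documents**
- Expected tablets: 1 per dosing time × 2 per day × 7 = 14 per week (SAP 7.1.2).
- Bottle: 30 tablets (Protocol 5.1.1).
- Visit interval after Week 15: 13 weeks (Protocol 3.1), so 13 × 14 = 182 tablets.
- Compliant band: 80% to 105%.
- Largest tablet: 18 mg (Protocol 5).

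**Assumptions**
- The test patient takes every dose, one tablet twice daily (true compliance 100%), and returns everything except the containers stated.
- Seven bottles (210 tablets) are dispensed per 13-week interval: 182/30 = 6.07, rounded up. The protocol mentions overage without a number.
- How often bottles go unreturned is not in the documents, so ranges are shown.

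**1. Discarded empty bottles.** With k bottles unreturned over T weeks, compliance = 100 × (14T − 30k)/(14T). It falls below 80% when 30k exceeds 20% of 14T.

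| Weeks treated | Expected tablets | One bottle lost | Bottles needed to fall below 80% |
|---|---|---|---|
| 15 | 210 | 85.7% | 2 (71.4%) |
| 28 | 392 | 92.3% | 3 (77.0%) |
| 54 | 756 | 96.0% | 6 (76.2%) |
| 106 | 1484 | 98.0% | 10 (79.8%) |
| 158 | 2212 | 98.6% | 15 (79.7%) |

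A single bottle is enough only when 30/(14T) > 0.20, that is, for treatment shorter than 30/(0.20 × 14) = 10.7 weeks.

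**2. Last supply never returned.** The last visit is at week V and the patient stops w weeks later. The SAP rule gives 100 × 14V/[14(V + w)]. Dispensed minus returned gives 100 × (14V + 210)/[14(V + w)].

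| Last visit | SAP rule, w = 2 / 6.5 / 13 | Dispensed minus returned, w = 2 / 6.5 / 13 |
|---|---|---|
| Week 15 | 88.2 / 69.8 / 53.6% | 176.5 / 139.5 / 107.1% |
| Week 28 | 93.3 / 81.2 / 68.3% | 143.3 / 124.6 / 104.9% |
| Week 41 | 95.3 / 86.3 / 75.9% | 130.2 / 117.9 / 103.7% |
| Week 54 | 96.4 / 89.3 / 80.6% | 123.2 / 114.0 / 103.0% |
| Week 106 | 98.1 / 94.2 / 89.1% | 112.0 / 107.6 / 101.7% |

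The true value is 100% throughout. With one 13-week supply lost, a result below 80% requires 13/T > 0.20, so total treatment under 65 weeks.

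**3. Doses above 36 mg/day.** With an 18 mg maximum strength, one tablet twice daily delivers at most 36 mg. Higher daily doses need at least two tablets per dosing time against an expected one. At two tablets, full adherence scores 200%. With a share f of tablets unreturned the score is 200 × (1 − f), which is below 80% only when f > 0.60. In this group the denominator pushes the figure the other way, and by more.

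**The case against.** The strongest defence is that the SAP fills a gap. The protocol is silent on unreturned containers, the SAP keeps its formula, and the SAP Introduction allows extra detail and promises that differences will be explained. Scoring missing bottles as unused is a cautious convention. Protocol 3.1 encourages retention of unused containers, 5.4 requires empty ones to be accounted for, and 6.3.3 collects all study drug at early termination, so losses may be few. All of this stands, and it makes the Section 9 omission a documentation matter. It does not change the direction of the rule or its effect on a short-treated patient.

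Three stronger readings are tempting, and the documents support none of them.
- **That patients who discard bottles or drop out are generally tabulated below 80%.** The result depends on the 20% threshold. Dropping out alone lowers nothing, because the denominator covers only the patient's own treatment period. That emptied bottles are the likeliest to be thrown away is plausible but appears nowhere in the documents.
- **That the protocol formula is right and should simply be restored.** It counts a dropout's untaken tablets as used. For a last visit at Week 28 and a stop two weeks later it gives 143.3% against the SAP's 93.3%, and here the SAP is closer to the true 100%.
- **That the safety or efficacy results depend on this figure.** No analysis population, patient-year calculation or test uses compliance. Dose and treatment duration are tabulated separately, and Protocol 6.4 takes a pharmacokinetic sample at the Post-withdrawal Visit.

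**Conclusion.** The concern holds in limited form. As written, the bottle rule can only lower compliance, contradicts the formula it qualifies, applies to one container type and is not declared in Section 9. For an adherent patient on one tablet twice daily it produces a false below-80% entry only when more than 20% of expected tablets are in unreturned bottles. That is realistic for patients who leave within about 65 weeks having used but not returned most of a 13-week supply, and for repeated loss of bottles. Single losses at Week 15 or later, and later dropouts, stay at or above 80%.

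The number of patients affected cannot be estimated from the documents. The percentages rest on full true adherence and, for the dispensed-minus-returned column, on seven bottles per interval. The consequence is confined to a descriptive table. The one-tablet denominator is a separate fault in the same section that works in the opposite direction, so the two should be corrected together.

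**What to change.** In SAP 7.1.2, stop using the zero-use assumption as the sole rule.

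1. Report the number of patients with any unreturned container and the number of containers not returned.
2. Present the compliance summary, continuous and categorical, under both extremes: unreturned containers fully unused, and fully used. These are bounds, not estimates.
3. Apply the same rule to blister packs and bottles.
4. List the rule in SAP Section 9.
5. Replace the one-tablet denominator with the number of tablets per dosing time that the patient's assigned dose required, so that the bounds mean the same thing above and below 36 mg/day.

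Assigning dosing days to individual bottles is not needed. Several bottles cover one interval, and the documents describe no link from bottle to day, so such a calculation may not be possible.

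The cost is a somewhat larger table and minor programming. The present rule already requires unreturned bottles to be identified, so the count in item 1 should need no new data for bottles; for blister packs the documents do not say whether this is recorded. Item 5 needs the dose history, which the SAP already summarises by visit.

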## 5. STUDY TREATMENT

The study drug to be used in this trial is a tablet formulation of SD-809. Five dosage strengths of SD-809 will be available for use: 6, 9, 12, 15, and 18 mg tablets. The actual dose of SD-809 received by the subject will be determined by the clinical pack supplied. The initial drug supply will be provided to the subject in the clinic at the Baseline visit.

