### 5.2. Treatment Regimen

#### 5.2.1. General Guidelines

The following general guidance applies to treatment regimens for all subjects in the study:

- All treatment regimens will be administered BID with meals, approximately 10 hours apart during the day.
- The starting dose will be SD-809 12 mg/day (6 mg BID) regardless of previous treatment in the parent study. Prior treatment assignment from the parent study will remain blinded.

- For subjects with body weight less than 100 kg, the maximum total daily dose of SD-809 is 48 mg/day (24 mg BID), unless the subject is on a strong CYP2D6 inhibitor (paroxetine, fluoxetine, or bupropion), in which case the maximum daily dose is 36 mg/day. For subjects with body weight 100 kg or more, the maximum total daily dose of SD-809 is 60 mg/day (30 mg BID), unless the subject is on a strong CYP2D6 inhibitor (paroxetine, fluoxetine, or bupropion), in which case the maximum daily dose is 42 mg/day.

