**Table 2: Maximum Daily Dose Level During the Maintenance Period**

Body weight (kg)*	Target dose (schedule)	
	Not CYP2D6 impaired	On strong CYP2D6 inhibitor
<100 kg	48 mg/day (24 mg BID)	36 mg/day (18 mg BID)
≥100 kg	60 mg/day (30 mg BID)	42 mg/day (21 mg BID)

\*Body weight at the time of dose increase >48 mg/day

- Daily doses will be administered according to instructions provided in the Pharmacy Manual.
- During the titration period, the dose of SD-809 should be increased on a weekly basis in increments of 6 mg of the total daily dose until:
  - There is adequate control of dyskinesia;
  - The subject experiences a protocol-defined clinically significant adverse event (defined as related to study drug and either a) moderate or severe in intensity or b) meets the criteria for a serious adverse event); or
  - The maximal allowable dose is reached.
- Study drug will be titrated over the initial 6 weeks of therapy, if necessary, to identify a dose that provides adequate dyskinesia control and is well tolerated. Changes in dose should not be made more often than once per week unless the subject is experiencing an intolerable adverse event.
- If a subject experiences a clinically significant adverse event attributable to SD-809, the Investigator will determine if a dose reduction or dose suspension, or withdrawal from the study is necessary.

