**The reason for a dose reduction, suspension, or discontinuation must be clearly documented.**

**5.3. Treatment Administration**

Each tablet should be swallowed whole with water and not broken, crushed, or chewed. Tablets should be taken with food and not be taken on an empty stomach.

Subjects should be instructed to take the study drug with meals: tablets will be administered BID with meals in the morning and evening, as indicated on drug packaging. It is recommended that BID doses be taken approximately 10 hours apart during the day. A minimum of 6 hours should elapse between doses. If a subject misses a dose and it is within 6 hours of their next dose, the missed dose should be skipped.

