## **INTRODUCTION**

This Statistical Analysis Plan (SAP) describes the planned analysis and reporting for Teva Branded Pharmaceutical Products R&D, Inc. study SD-809-C-20 (An Open-Label, Long-Term Safety Study of SD-809 [Deutetrabenazine] for the Treatment of Moderate to Severe Tardive Dyskinesia), and was written in accordance with SOP GBP\_RD\_702 (Statistical Analysis Plan).

The reader of this SAP is encouraged to read the study protocol for details on the conduct of this study, the operational aspects of clinical assessments, and the timing for completing the participation of a patient in this study.

The SAP is intended to be in agreement with the protocol, especially with regards to the primary and all secondary endpoints and their respective analyses. However, the SAP may contain more details regarding these particular points of interest, or other types of analyses (eg other endpoints). When differences exist in descriptions or explanations provided in the study protocol and this SAP, the SAP prevails; the differences will be explained in the Clinical Study Report.

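### The SAP compliance denominator allows one tablet per dosing time, but any dose above 36 mg/day needs more, so compliance is overstated in proportion to time above 36 mg/day

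*SAP*

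**What the plan says.** SAP section 7.1.2 defines percent compliance as 100 times tablets used over tablets expected. Tablets used are those dispensed minus those returned. Tablets expected are counted from the morning and evening dosing times, on the basis that "1 tablet is used for each dosing time point"; dose level does not enter. A patient counts as compliant at 80% to 105%, and the results are tabulated as <80%, 80% to 105% and >105%. The section adds a rule for missing bottles: "If a patient does not return the pill bottle, it will be assumed that the patient took no study medication from that bottle".

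The protocol supplies the facts that this rule has to fit. Section 5 states: "Five dosage strengths of SD-809 will be available for use: 6, 9, 12, 15, and 18 mg tablets". Section 5.3 states: "Each tablet should be swallowed whole with water and not broken, crushed, or chewed". Section 5.2.1 sets twice-daily dosing throughout. Table 2 gives maximum doses of 48 mg/day below 100 kg and 60 mg/day at 100 kg or more, or 36 and 42 mg/day on a strong CYP2D6 inhibitor.

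Protocol section 5.5 uses the same ratio and the same 80% to 105% limits, but only says tablets used are "divided by the expected number of tablets to be used". It has no one-tablet rule. The SAP Introduction settles conflicts: "When differences exist in descriptions or explanations provided in the study protocol and this SAP, the SAP prevails". SAP section 9 lists a single departure from the protocol, on ECG variables, and does not mention compliance.

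**The concern.** Numerator and denominator are in different units once a patient takes more than one tablet at a dosing time. The numerator counts tablets; the denominator in effect counts dosing times. The same SAP section plans dose categories of >36 to ≤48 mg and >48 mg, so it expects doses that its compliance rule cannot represent.

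At stake is the only compliance summary in the SAP. It covers Parts A and B combined, and section 7.2.2 for Part B reports total daily dose only. An error that grows with time at high dose would show adherent high-dose patients as overusing study drug. It could also class patients who took too little as compliant. A reader could not undo this from the table, because f is not shown by patient.

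**Working it through.** **Inputs.** Strengths 6, 9, 12, 15 and 18 mg (Protocol 5). Tablets whole (5.3). Twice daily (5.2.1). Start: "The starting dose will be SD-809 12 mg/day (6 mg BID) regardless of previous treatment in the parent study". Titration in steps of 6 mg/day, at most weekly (5.2.1). Highest dose 60 mg/day (Table 2). End of Part A at Week 158.

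**Step 1: the SAP's figure of one tablet.** Smallest number of tablets per dosing time = ceil((daily dose / 2) / 18), assuming equal morning and evening doses. Every count was confirmed by listing tablet combinations.

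| Daily dose (mg) | Per dosing time (mg) | Fewest tablets |
|---|---|---|
| 12, 18, 24, 30, 36 | 6, 9, 12, 15, 18 | 1 |
| 42 | 21 | 2 (12 + 9) |
| 48 | 24 | 2 (12 + 12) |
| 54 | 27 | 2 (15 + 12) |
| 60 | 30 | 2 (15 + 15) |

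The SAP's figure is reproduced up to 2 × 18 = 36 mg/day and fails at every step above.

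**Step 2: the inflation factor.** Let D be the number of dosing times and f the share above 36 mg/day. With one tablet at or below 36 mg/day and two above, the correct denominator is D(1 − f) + 2Df = D(1 + f). The SAP uses D. For any numerator, therefore:

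SAP percentage = correct percentage × (1 + f)

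**Step 3: effect on the categories, with all bottles returned.**

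- Full adherence scores 100(1 + f)%. It passes 105% when f > 0.05.
- Half adherence scores 50(1 + f)%. It reaches 80% when f ≥ 0.60. At f = 0.50 it scores 75% and is still correctly non-compliant.
- True adherence of 80% scores 80(1 + f)%. It passes 105% when f > 105/80 − 1 = 0.3125. Beyond that point, everyone who truly took at least 80% is moved to >105%.
- True adherence labelled compliant runs from 80/(1 + f) to 105/(1 + f). That is 64.0% to 84.0% at f = 0.25 and 53.3% to 70.0% at f = 0.50.

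**Step 4: the largest f that the titration permits.** Weeks 1 to 5 at 12, 18, 24, 30 and 36 mg/day, then above 36 mg/day from week 6 onward. Over T weeks, f = (T − 5)/T.

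| T (weeks) | f | Full adherence scores | Half adherence scores | True adherence labelled compliant |
|---|---|---|---|---|
| 6 | 1/6 = 0.167 | 116.7% | 58.3% | 68.6% to 90.0% |
| 15 | 10/15 = 0.667 | 166.7% | 83.3% | 48.0% to 63.0% |
| 54 | 49/54 = 0.907 | 190.7% | 95.4% | 41.9% to 55.0% |
| 158 | 153/158 = 0.968 | 196.8% | 98.4% | 40.6% to 53.3% |

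As a check in tablets over 158 weeks: the SAP expects 158 × 14 = 2,212. The patient needs 14 × (5 + 2 × 153) = 4,354, and 4,354/2,212 = 1.968. A score of 200% is a limit that is not reached.

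On this path, full adherence leaves the band after 5/0.95 = 5.3 weeks, and half adherence enters it from 5/0.40 = 12.5 weeks.

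**The case against.** The best case against this is that little depends on it. Compliance feeds no endpoint, analysis set, p-value or adverse event rate, and the SAP defines no per-protocol set. On-study monitoring follows Protocol 5.5, which does not assume one tablet. All of that stands, and it limits the point to one descriptive summary.

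The percentages over long treatment are extremes. They need the fastest titration, a sustained dose above 36 mg/day and every bottle returned, while the protocol stops increases once dyskinesia is adequately controlled. This also stands. The thresholds in f are the sturdier result, and patients who never exceed 36 mg/day on one tablet per dosing time are not affected by this rule.

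Tablet configuration is left to the Pharmacy Manual, and no split is stated for 54 mg/day, which Table 3 allows. An uneven 18 + 36 mg split would use three tablets a day, a factor of 1.5 instead of 2. That trims the figure at that dose only, since Table 2 states equal splits for 42, 48 and 60 mg/day. Whatever the manual says, any dose above 36 mg/day puts more than 18 mg in at least one dosing time, so one tablet each time cannot suffice.

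Unreturned bottles are scored as nothing taken, so a patient's reported figure may still come out too low. That is a separate error in the other direction. Against a correct denominator the factor remains 1 + f.

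**Conclusion.** The concern holds. As written, the rule gives a wrong compliance mean and wrong category counts whenever patients spend time above 36 mg/day. The overstatement factor relative to a correct denominator is 1 + f: none at f = 0, 1.5 at f = 0.50, and at most 1.968 over 158 weeks on the permitted titration. Misclassification runs both ways: adherent patients go to >105%, and some who took too little count as compliant.

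These sizes assume one tablet per dosing time at or below 36 mg/day, two above, equal morning and evening doses, and all bottles returned. The number of patients affected cannot be estimated, because the documents give no dose distribution. The primary analysis in Part B and all other planned safety outputs are untouched. The SAP should be corrected before the final Part A and B analyses.

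**What to change.** In SAP section 7.1.2, drop the one-tablet assumption. Define tablets expected as the sum, over scheduled dosing times, of the tablets in the regimen dispensed at the dose level assigned on that date. Take this from the IRT and dispensing records, and reconcile it with Protocol 5.5 and the Pharmacy Manual. Do not hard-code tablet counts by dose. Keep the 80% to 105% limits.

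The cost is one SAP sentence and one derivation, with no effect on patients or on any other analysis. Tablets dispensed and returned are already collected, and Protocol 5.2.5 refers to dose levels assigned through IRT. One thing needs confirming: the dispensing log in Protocol 5.4 is described as holding subject, date and quantity, so the team should check that strength or tablets per dose can be recovered by date.
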